[figure not shown]
[figure not shown]
[figure not shown]
[figure not shown]

Protocol for non-interventional studies based on existing data

Document Number:	c30035684-01
BI Study Number:	1237-0092
BI Investigational Product(s):	Not applicable
Title:	Real-world treatment of newly diagnosed COPD patients: A retrospective German claims data analysis
Protocol version identifier:	1.0
Date of last version of protocol:	16 October 2019
PASS:	No
EU PAS register number:	Not applicable
Active substance:	ATC code group R03
Medicinal product:	Not applicable
Product reference:	Not applicable
Procedure number:	Not applicable
Joint PASS:	No
Research question and objectives:	
 A. Description of the real-life drug treatment of patients with incident COPD, including description of treatment sequence/escalation in the first 12/24/36 months after incident diagnosis B. Comparison of initial drug treatment of incident COPD patients with two versions of German treatment guidelines (2012/2018) C. Description of exacerbation frequency (severe exacerbations associated with an inpatient hospitalization) of incident COPD patients in the first 12/24/36 months after incident diagnosis

Proprietary confidential information © 2019 Boehringer Ingelheim International GmbH or one or more of its affiliated companies

	D. Description of health-care resource use (HCRU; including use of oxygen therapy) and direct treatment cost of incident COPD patients in the first 12/24/36 months after incident diagnosis 
Country(-ies) of study:	Germany
Author:	
Marketing authorisation holder(s):	
MAH contact person:	
In case of PASS, add: <EU-QPPV:>	Not applicable
In case of PASS, add: <Signature of EU-QPPV:>	Not applicable
Date:	16 October 2019

Page 1 of 58

Proprietary confidential information

© 2019 Boehringer Ingelheim International GmbH or one or more of its affiliated companies. All rights reserved.
This document may not - in full or in part - be passed on, reproduced, published or otherwise used without prior written permission

2. LIST OF ABBREVIATIONS

ADR	Adverse Drug Reaction
AE	Adverse Event
AESI	Adverse Event of Special Interest
ATC	Anatomical Therapeutic Chemical / Defined Daily Dose Classification
BI	Boehringer Ingelheim
BMI	Body-Mass-Index
CAT	COPD Assessment Test
CCI	Charlson Comorbidity Index
CI	Confidence Interval
COPD	Chronic obstructive pulmonary disease
CRO	Clinical Research Organization
DALYs	Disability-Adjusted Life Years
DDD	Defined Daily Dose
DMP	diseases management program
EBM	Einheitlicher Bewertungsmaßstab
ENCePP	European Network of Centres for Pharmacoepidemiology and Pharmacovigilance
EU PAS (register)	European Union electronic Register of Post-Authorisation Studies
FEV(1)	Forced expiratory volume (in 1 second)
GLM	Generalized Linear Model
GOLD	Global initiative for chronic obstructive lung disease
GONr	Gebührenordnungs-Nr.
GP	General Practitioners
GPP	Good Pharmacoepidemiology practices
GVP	Good pharmacovigilance practices
HCER	Health care resource use
HRQoL	Health-related quality of life
IC	Informed Consent
ICD	International Statistical Classification of Diseases and Related Health Problems
ICH-GCP	International Council for Harmonization of Technical Requirements for Pharmaceuticals for Human Use
ICS	Inhaled corticosteroids
IEC	Independent Ethics Committee
ISPE	International Society for Pharmacoepidemiology
ISPOR	International Society for Pharmacoeconomics and Outcomes Research
KM	Kaplan-Meier
LABA	Long-acting beta agonist
LAMA	Long-acting muscarinic antagonist
LOCF	Last observation carried forward

LTOT	Long-Term Oxygen Therapy
MedDRA	Medical Dictionary for Drug Regulatory Activities
mMRC	Modified Medical Research Council
NIS	Non-interventional study
OPS	Operationen- und Prozedurenschlüssel
PASS	Post-authorisation safety study
PhRMA	Pharmaceutical Research and Manufacturers Association
PY	Patient year
PZN	Pharmazentralnummer
QALYs	Quality added life years
SABA	Short-acting beta antagonist
SAMA	Short-acting muscarinic antagonist
SD	Standard Deviation
SI	Study Investigator
WHO	World-Health Organization

4. ABSTRACT

Name of company: Boehringer Ingelheim			
Name of finished medicinal product: COPD medication of any type			
Name of active ingredient: COPD medication of any type, ATC code R03			
Protocol date: 16 Oct 2019	Study number: 1237-0092	Version/Revision: 1.0	Version/Revision date: Not applicable
Title of study:	Real-world treatment of newly diagnosed COPD patients: A retrospective German claims data analysis		
Rationale and background:	
In terms of COPD drug therapy, the current German COPD guideline (S2) [1, 2] recommends a treatment escalation procedure. For incident COPD patients (for the sake of simplicity, newly diagnosed and so far treatment naïve COPD patients will be referred to as “incident COPD patients” in the following), the German guideline recommends the following:
 
 • No treatment (low symptom burden) • SABA or SAMA • LABA or LAMA or LABA+LAMA. 
All other treatments, particularly combination treatments including ICS¹, are only recommended as escalation therapy.
 
Currently, knowledge on real world treatment of incident COPD patients in Germany is sparse, in particular regarding the frequency of different drug therapy prescriptions and the frequency of early therapy escalation including ICS.
 
This study aims to address this issue by reporting treatment of incident COPD patients in the real world. COPD and treatment associated outcomes, especially severe exacerbations (leading to hospitalization), health-care resource use, and early use of oxygen therapy, will be explored. In addition, real-world treatment of incident COPD patients will be compared to German guidelines, using current 2018 guidelines and 2012 guidelines as framework in two scenario calculations.
		

¹ ICS is recommended by the guideline for COPD patients with an asthmatic component. Based on inclusion/exclusion criteria as applied in this study, these patients will be excluded from analysis.

Name of company: Boehringer Ingelheim			
Name of finished medicinal product: COPD medication of any type			
Name of active ingredient: COPD medication of any type, ATC code R03			
Protocol date: 16 Oct 2019	Study number: 1237-0092	Version/Revision: 1.0	Version/Revision date: Not applicable
Research question and objectives:	
A. Description of the real-life drug treatment of patients with incident COPD, including description of treatment sequence/escalation in the first 12/24/36 months after incident diagnosis
 
B. Comparison of initial drug treatment of incident COPD patients with two versions of German treatment guidelines (2012/2018)
 
C. Description of exacerbation frequency (severe exacerbations associated with an inpatient hospitalization) of incident COPD patients in the first 12/24/36 months after incident diagnosis
 
D. Description of health-care resource use (HCRU; including use of oxygen therapy) and direct treatment cost of incident COPD patients in the first 12/24/36 months after incident diagnosis
		
Study design:	
A retrospective analysis will be done based on a claims dataset delivered by a German sickness fund (so far, a cooperation with [REDACTED] [REDACTED] (approximately 3.2 million insured persons) is planned; a second sickness fund might be included as well). The dataset will cover the period 01/01/2013-30/06/2018², and will only include patients who were continuously insured within the sickness fund between the entire period (death is the only exception)³. In selected analyses, incident COPD patients will be observed for an exact follow-up period of 12 months (in subgroup analyses: 24 and 36 months); censoring of patients will only be done in case a patient died during the respective follow-up period.
		

² If more data will be available until time of analysis start, further quarters (from 2018) will be included into the analysis. The Steering Board of the study will discuss whether it is meaningful to include additional data from 2010/2011/2012 taking into account that a ministry approval would be necessary in that case.

³ Continuous insurance is necessary, to not accidentally include patients twice in case they left the sickness fund intermediately and went back later on and are included within the dataset with two different pseudo numbers.

Name of company: Boehringer Ingelheim			
Name of finished medicinal product: COPD medication of any type			
Name of active ingredient: COPD medication of any type, ATC code R03			
Protocol date: 16 Oct 2019	Study number: 1237-0092	Version/Revision: 1.0	Version/Revision date: Not applicable
Population:	
The following inclusion criteria apply:
 
 • All patients who were continuously insured by the sickness fund for the entire period (01/01/2013-30/06/2018) or, in case a patient deceased after index date, for the time until death⁴ • A patient will be included as an incident COPD patient if either a hospital documented at least one COPD diagnosis (ICD-10 J 44.-) or a specialist (pneumologist) documented at least 2 confirmed COPD diagnoses (above ICD-10 code) in two different quarters; the first of the above diagnoses is defined as index diagnosis; inclusion period is defined as lasting from 01/01/2014 until 30/06/2017⁵ • Patients should not have received any COPD diagnosis (ICD-10 J44.-) or any COPD-associated medication (Suppl. Table 2⁶) in the 12 months pre-index period • Patient should have, at date of incident COPD diagnosis (index date), an age of at least 40 years 
In the planned analyses, different subpopulations with regard to follow-up time and availability of disease management program (DMP) data will be defined.
		

⁴ Patients censored due to their death will be included as well including reporting of their baseline characteristics.

[figure not shown]
⁵ Please note: Based on all patients with at least one confirmed outpatient or inpatient COPD diagnosis (from specialists, GPs and/or hospitals), an attrition chart will show how many patients are subsequently excluded because of the applied inclusion/exclusion criteria.

⁶ Prescription of systemic/oral corticosteroids (SCS/oral) will not be considered as exclusion criteria

Name of company: Boehringer Ingelheim			
Name of finished medicinal product: COPD medication of any type			
Name of active ingredient: COPD medication of any type, ATC code R03			
Protocol date: 16 Oct 2019	Study number: 1237-0092	Version/Revision: 1.0	Version/Revision date: Not applicable
Variables:	
Baseline characteristics (referring either to index date = date of incident (first) diagnosis of COPD, or to 12 months pre-index period)
 
 • Age • Gender • Concomitant diseases /comorbidity level 
 ○ Most frequently observed 10 diseases, based on recorded ICD-10 codes up to 3rd level ○ Charlson Comorbidity Index (CCI) ○ Percentage of patients with at least one confirmed inpatient or two confirmed outpatient diagnoses in two different quarters of the following diseases: 
 ▪ Asthma ▪ Bronchiectasis ▪ Bronchial carcinoma ▪ Diabetes mellitus ▪ Congestive heart failure ▪ Moderate to severe kidney disease ▪ Myocardial infarction ▪ Hypertension ▪ Peripheral vascular disease ▪ Cerebrovascular event or transient ischemic attack ▪ Hemiplegia ▪ Dementia ▪ Sleep apnoea ▪ Osteoporosis ○ Percentage of patients with at least one confirmed inpatient or two confirmed outpatient diagnoses in two different quarters of the following respiratory diseases: 
 ▪ ICD-10 codes J0-J99 (Top-5 diseases) 		

Name of company: Boehringer Ingelheim			
Name of finished medicinal product: COPD medication of any type			
Name of active ingredient: COPD medication of any type, ATC code R03			
Protocol date: 16 Oct 2019	Study number: 1237-0092	Version/Revision: 1.0	Version/Revision date: Not applicable

 Previous drug treatment in the pre-index period, based on appropriate ATC group level 
 Percentage of patients who received specific treatments (most common 10 treatments as observable for above samples) with at least two prescriptions in the pre-index period. 
Documentation referring to the 12 months follow-up after index date (for patient subgroups: 24 months/36 months follow-up, or complete follow-up period)
 
 For patients with available data resulting from a disease management program (DMP) 
 Weight [kg] (reported MIN, MAX and MEAN during follow-up period) Height [cm] Blood pressure (reported MIN, MAX and MEAN during follow-up period) Non-drug treatment recommendations Exacerbations (number and severity) FEV₁ (reported MIN, MAX and MEAN during follow-up period) Smoking status if applicable Drug treatment with long-acting bronchodilators (incl. separate reporting for respective agent classes beta-agonists, anticholinergics, methylxanthines) Drug treatment with short-acting agents Drug treatment with anti-inflammatory drugs (ICS, PDE-4, macrolides) Top-10 prescribed non-COPD drug therapies (based on ATC codes on appropriate level) 			

Name of company: Boehringer Ingelheim			
Name of finished medicinal product: COPD medication of any type			
Name of active ingredient: COPD medication of any type, ATC code R03			
Protocol date: 16 Oct 2019	Study number: 1237-0092	Version/Revision: 1.0	Version/Revision date: Not applicable

 • Antibiotics for systemic use (based on ATC J02AA) • Antibiotics in combination with corticosteroids (based on ATC D07C) • Systemic/oral corticosteroids (SCS/OCS; based on ATC R01AD02; D07AA01; D10AA02; H02AB04) • All-cause hospitalizations 
 ○ Among them: hospitalizations with COPD as main diagnosis (ICD-10 J44.-) • Among them: hospitalizations with a COPD exacerbation as main diagnosis (ICD-10 J44.1) • Exacerbations as documented by outpatient pneumologists (ICD-10 J44.1) • GP visits and pneumologists' visits and visits to other specialists • Prescription of COPD-associated aids 
 ○ Oxygen therapy • Date of death, if patient died during follow-up period (for censoring and time to event analyses). 			
Data sources:	This retrospective study is an analysis of an anonymized claims dataset provided by the [REDACTED] and potentially a second sickness fund (approval still pending).		
Study size:	
Based on an initial feasibility assessment done by [REDACTED] N>40,000 incident COPD patients meeting above inclusion/exclusion criteria can be expected.
 
 • Among them, about 26,000 (~65%) received at least one prescription of a long-acting bronchodilator in the 12 months follow-up period • Percentage of incident patients with at least one DMP documentation (providing more detailed information for additional analysis) is about 30%. Among the DMP patients, about 4,000 incident patients can be expected with at least one prescription of a long-acting bronchodilator in the 12 months follow-up period. It needs to be evaluated during the study whether the DMP data can be used for study purposes, which would require a start of DMP documentation early after the incident COPD diagnosis. 		

Name of company: Boehringer Ingelheim			
Name of finished medicinal product: COPD medication of any type			
Name of active ingredient: COPD medication of any type, ATC code R03			
Protocol date: 16 Oct 2019	Study number: 1237-0092	Version/Revision: 1.0	Version/Revision date: Not applicable
Data analysis:	
Descriptive statistics will mainly be applied in this study. For categorical (including dichotomous) variables, frequencies, percentages and 95% confidence intervals (CIs) will be reported, along with corresponding sample sizes. Continuous variables will be summarized using mean, standard deviation, median, ranges and 95% CIs along with corresponding sample sizes.Statistical comparisons of socio-demographic and clinical characteristics will be conducted between different patient groups, e.g. patients with different comorbidity profile or therapy. Comparisons will be done based on appropriate tests, e.g. Chi-square tests, Fisher's exact tests, t-tests or a suitable non-parametric tests.Time to event analyses will be done based on a Kaplan Meier (KM) methodology; comparisons between groups will be done using Log Rank tests.		
Milestones:	 A large rectangular area of the table is completely blacked out, indicating that the content has been redacted.		

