 - According to both above guidelines, a triple combination treatment LABA+LAMA+ICS should only be prescribed if a patient experienced at least 2 exacerbations or one severe exacerbation requiring an inpatient treatment in the history of the disease. In addition, the 2012 guideline also recommended such a treatment in case a FEV₁<50% could be observed. Based on this, the following percentages will be reported:
 - Percentage of patients not treated in line with the 2018 guideline
 - Only one or no confirmed outpatient diagnosis and no inpatient diagnosis of a COPD exacerbation (ICD-10 J44.1) before date of prescription of a triple therapy.
 - Percentage of patients not treated in line with the 2012 guideline
 - Only one or no confirmed outpatient diagnosis and no inpatient diagnosis of a COPD exacerbation (ICD-10 J44.1) and only one or no outpatient diagnosis and no inpatient exacerbation diagnoses as documented in the DMP dataset and no documented FEV₁ value <50%.

Second Secondary

Description of exacerbation frequency

For all samples (COPD-12, COPD-24, COPD 36, COPD DMP-12, COPD DMP-24, COPD DMP-36, COPD-FULL DATA), exacerbation frequency in the pre-defined follow-up periods (12 months, 24 months, 36 months, patient-individual follow-up times) will be described. Because of the higher diagnosis validity, in the main analysis only severe exacerbations leading to an inpatient hospitalization (COPD exacerbation documented as main diagnosis: ICD-10 J44.1) will be considered. Moreover, in a separate analysis proxies will be used to estimate non-severe exacerbations. Therefore prescriptions of SCS/OCS either separately or in combination with antibiotics, will be considered as proxy for the treatment of a non-severe exacerbation (without an inpatient hospitalization). Exacerbation frequency (once for severe and once for non-severe exacerbations) will be reported as percentage of patients having experienced at least 1 exacerbation, exactly 1 exacerbation, exactly 2 exacerbations, exactly 3 exacerbations, and >3 exacerbations, and as mean number of exacerbations per observed patient-year.

Third Secondary

Description of health care resource use and direct treatment cost

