Health care resource use (HCRU) and direct cost will be reported as described in Table 3, based on the perspective of a German sickness fund and based on prices of the respective years as reported in the claims data base. HCRU and cost will be reported for the following samples in separate analyses: COPD-12, COPD-24, and COPD-36.

Generally, HCRU/cost will be reported per observed patient year. HCRU and cost will be compared between the following patient groups:

- Patients participating in a DMP versus those who did not participate
- Patients having received early (first 3 months after index date) a triple combination therapy (LABA+LAMA+ICS) versus those who did not.

[figure not shown]
In a separate analysis based on COPD-36 sample, cost during the first year after incident COPD diagnosis will be compared with costs in the second and third year after incident diagnosis.

[figure not shown]
[figure not shown]
Table 3 HCRU and direct healthcare cost definition

Item	HCRU	Cost
COPD medication	
• Nb. of prescriptions for medications as reported in Suppl. Table 2, per agent type• Nb. of prescribed DDDs for medications as reported in Suppl. Table 2, per agent type	
• Drug cost (based on list prices) for medications as reported in Suppl. Table 2.
Other medications	
• Nb. of non COPD-medications, defined as at least 2 prescriptions of an agent (on third level of ATC groups)• Antibiotics for systemic use (ATC J02AA) and antibiotics in combination with corticosteroids (ATC D07C)	
• Drug cost of prescribed non-COPD medications
Outpatient treatment	
• Nb. of GP visits• Nb. of pneumologist visits• Nb. of other outpatient specialist visits	
• Cost of outpatient visits as defined in the HCRU column, based on the proxy of “treatment points”
Hospitalizations	
• Nb. of hospitalizations with a COPD-exacerbation (J44.1) including mean duration of stay in days• Nb. of hospitalizations with any COPD diagnosis as main diagnosis (J44.-) including mean duration of stay• Other non-COPD hospitalizations including mean duration of stay in days• Time to first all-cause hospitalization	
• Cost for hospitalizations as defined in the HCRU column

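### The ATC codes given for systemic antibiotics (J02AA) and two of those given for systemic/oral steroids (D07AA01, D10AA02) do not match their labels, which affects the separate non-severe exacerbation count and the antibiotic line of Table 3

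*Combined protocol and SAP*

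**What the plan says.** The Abstract (Variables, follow-up documentation) gives three code lists:

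- The first covers antibiotics alone: "Antibiotics for systemic use (based on ATC J02AA").
- The second covers products that join an antibiotic to a steroid: "Antibiotics in combination with corticosteroids (based on ATC D07C").
- The third covers the steroids themselves: "Systemic/oral corticosteroids (SCS/OCS; based on ATC R01AD02; D07AA01; D10AA02; H02AB04").

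Table 3 in section 9.3.2.2 carries the same antibiotic codes as a resource-use item under other medications: "Antibiotics for systemic use (ATC J02AA) and antibiotics in combination with corticosteroids (ATC D07C"). Supplemental Table 2 has a class for systemic/oral corticosteroids, with prednisolone under R01AD02 and methylprednisolone under D07AA01 and D10AA02. The methylprednisolone entry ends in a semicolon, so a further code may have been lost when the PDF was read.

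The proxy is set out under the second secondary outcome in section 9.3.2.2: "prescriptions of SCS/OCS either separately or in combination with antibiotics, will be considered as proxy for the treatment of a non-severe exacerbation". That text names no codes. It belongs to a separate analysis, because "in the main analysis only severe exacerbations leading to an inpatient hospitalization" are considered, identified by J44.1 as main diagnosis.

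**The concern.** A claims analysis measures whatever its codes select. If a code labelled as a systemic antibiotic selects something else, and codes labelled as systemic steroids select skin products, then every variable built on them is mismeasured. A larger cohort does not help: with more than 40,000 expected patients the interval around a miscoded rate is narrow, but it is centred on the wrong value.

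Two outputs are at stake. One is the non-severe exacerbation frequency, reported as the distribution of event counts per patient and as a mean rate per patient-year. The other is the antibiotic item in Table 3. Because the antibiotic code appears in both the Abstract and Table 3, it is unlikely to be a typing slip in one place.

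**Working it through.** The documents give no proxy event rate, proxy sensitivity or prescription count by code, so there is no figure of the plan to reproduce. The check sets the lists beside the labels and then traces them through the proxy rule.

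**1. Labels against codes.** The last column is the ATC reading, which is an assumption to be checked against the index.

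| Label in the plan | Code | Where | ATC reading |
|---|---|---|---|
| Systemic antibiotics | J02AA | Abstract; Table 3 | antimycotics; systemic antibacterials are J01 |
| Antibiotic with corticosteroid | D07C | Abstract; Table 3 | topical combination; the label fits |
| Systemic/oral corticosteroid | D07AA01, D10AA02 | Abstract; Suppl. Table 2 | dermatological methylprednisolone |
| Systemic/oral corticosteroid | H02AB04 | Abstract | systemic methylprednisolone; the label fits |

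**2. What the documents show on their own.** The protocol uses the three-character group R03 for COPD medication as a whole. In Supplemental Table 2, five-character stems are much narrower: the R03BA codes are all inhaled steroids and the R03BB codes are all inhaled antimuscarinics. By the plan's own usage, J02AA is therefore one small subgroup and cannot cover systemic antibiotics in general. The list of abbreviations expands ATC as an anatomical classification, yet the single label systemic/oral draws codes from three main groups (R, D and H). This makes the lists doubtful without any outside source. The specific contents of J02, D07 and D10 come from the classification.

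**3. Effect on the proxy.** Let S be a prescription on the SCS/OCS list and A one on the antibiotic list. The rule counts S alone, or S with A. In logic, S or (S and A) equals S.

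- *Antibiotic code.* The total depends on S only. Replacing A by a wrong code adds and removes no event. It changes only whether an event is recorded as accompanied by an antibiotic.
- *Steroid codes.* Each D07AA01 or D10AA02 prescription satisfies S and can count as a non-severe exacerbation. Let D be the number of such prescriptions, H the number under H02AB04 and R the number under R01AD02. The share of list prescriptions that are dermatological is D / (D + H + R). It is 0% if D = 0 and approaches 100% as D comes to dominate. The documents give none of the three counts.
- *Omissions.* In Supplemental Table 2 a seven-character code identifies one agent. H02AB04 is the only H02 code in the visible lists, so systemic steroids under other H02AB codes (M prescriptions) are not counted. D raises the total and M lowers it, so the net error has no fixed sign.

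**4. Effect on Table 3.** The antibiotic item counts J02AA directly, so it reports a different drug group from the one it names.

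**5. What is not touched.** Severe exacerbations come from inpatient J44.1 and use no drug code. Cohort entry excludes patients with pre-index medication from Supplemental Table 2, but footnotes in the Abstract and in section 9.2 exempt SCS/OCS. The visible table contains no antibiotics.

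**The case against.** The strongest objection is that the documents never state what J01, J02, D07, D10 or H02AB contain. The internal argument shows that J02AA is narrow, but not that it is antimycotic. This stands as a limit on the evidence. However, the protocol adopts ATC as its coding system, so reading its codes by that system is fair, and the sponsor can confirm it in minutes.

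A reader might infer that the proxy loses nearly all its events because the antibiotic code finds no exacerbation courses. The documents do not support this. Steroids alone qualify, and the visible text reports one frequency for severe and one for non-severe events. It does not clearly commit to a separate count of steroid-plus-antibiotic courses, so a near-total loss would concern a quantity that the plan does not clearly report.

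A reader might also infer that D07C is mislabelled as systemic. It is not. Its label says only that an antibiotic is combined with a corticosteroid. The valid point is narrower: a topical combination does not mark an exacerbation course. Because the proxy wording also speaks of steroids in combination with antibiotics, the plan should say that D07C is not meant.

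Finally, macrolides are a reporting line ("Drug treatment with anti-inflammatory drugs (ICS, PDE-4, macrolides")) with no code in the visible text. That is missing detail and not an error, and some parts of the plan are redacted. The cut-off methylprednisolone row in Supplemental Table 2 is likewise not counted against the plan.

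**Conclusion.** The point holds in limited form. As written, J02AA does not identify systemic antibiotics, and D07AA01 and D10AA02 do not identify systemic/oral steroids. The D codes add false non-severe exacerbations to the total. J02AA misclassifies whether a steroid course came with an antibiotic and makes the antibiotic line of Table 3 wrong.

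No size can be given, because it depends on prescription counts by code that the documents do not contain. The conclusion rests on two assumptions: that the codes carry their ATC index meanings, and that the unnamed drugs in the proxy are those of the Abstract's lists. The main severe-exacerbation analysis and the selection of the cohort stand as they are. The matter therefore concerns one separate secondary analysis and one resource-use item.

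**What to change.** Before the extraction list is agreed with the sickness funds:

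1. In the Abstract and in Table 3, replace J02AA by the systemic antibacterial group J01.
2. Remove D07AA01 and D10AA02 from the SCS/OCS list in the Abstract and from the systemic/oral corticosteroid row of Supplemental Table 2. Define SCS/OCS by the systemic corticosteroid group H02AB in both places. R01AD02 should be checked at the same time, since Supplemental Table 2 lists other R01AD codes as inhaled steroids.
3. In section 9.3.2.2, name the code lists that the proxy uses and state that D07C is not among them.
4. Do not add J01 to Supplemental Table 2. That table defines the pre-index exclusion medication, and the exemption covers SCS/OCS only. Any antibacterial in the 12 months before index would then exclude a patient.
5. Check every changed code against the ATC index and record the version used.

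The cost is a code-list edit and matching changes to the extraction manual. No new data source is needed, and cohort selection does not change.
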